6.0 STATISTICAL PLAN

This sample size is small enough to feasibly recruit over the given time period, yet large enough to correlate differences between the two groups. Antero-posterior pelvis and lateral hip radiographs will show patterns of stress-shielding, and the EBRA-FCA method provides a non-invasive means of measuring the extent of implant migration (if any). Patient-reported outcomes will be used to determine the effect of each implant on the patients' daily lives. Routine follow-up over 2 years is necessary to determine the long-term impact of each implant.

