Although the standard-length proximally coated titanium tapered wedge has a successful long-term track record, its design leaves room for improvement (Mallory et al 2001, Marshall et al 2004). Standard length stems cause stress-shielding in Gruen zones 1 and 7, suggesting that the diaphyseal portion of a stem may interfere with proximal loading (Gibbons et al 2001, Schmidt et al 2004). Even proximally coated flat tapered stems are subject to diaphyseal loading (Cooper et al 2011). The Accolade stem has been associated with significant early subsidence, especially in males with Dorr type A hips (Jacobs & Christensen 2009). This suggests that the stem may wedge distally, thereby interfering with osseointegration (White et al 2012). By achieving a purely metaphyseal fit, short stems can prevent excessive bone loss secondary to stress shielding (Gustke 2012). We believe short stems are an equally effective alternative to traditional tapered stems in THA; however, long-term studies are essential to proving their efficacy.

Long-term studies of short stems are lacking in current literature. With respect to initial stability and bony ingrowth, short-term data is promising; however, there is still potential

for late aseptic failure (Capello et al 2009, Kroell et al 2009, Morales de Cano et al 2013, Schmidutz et al 2012). By conducting a single blinded, prospective, randomized investigation of two stems of varying length with equal metallurgy, coating, and proximal geometry, we can identify the effects of stem length on long-term outcomes.

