5.0 STUDY DESIGN & METHODS

50 patients will be recruited over 12-18 months. Half of the patients will receive the Taperloc Microplasty short femoral stem, while the other half will receive the standard-length Taperloc stem. Patients will be randomized in the operating room through the opening of opaque, study-numbered envelopes during preparation of the femur.

Immediate weight bearing will be allowed post-operatively. Patient-reported outcomes, as well as x-ray analysis, will be administered immediately post-operatively, 6 weeks post-operatively, 3 months post-operatively, 6 months post-operatively, 12 months post-operatively, and 2 years post-operatively. X-ray analysis includes antero-posterior pelvis, and lateral hip radiographs. The X-rays will be sent to [name] at the University of Innbruck, Austria for analyses using the EBRA-FCA software. Patient-reported outcomes will be measured using the Harris Hip and SF-36 questionnaires.

Procedures such as X-rays will be used during this research study to see how the patient is doing. The cumulative radiation exposure from these tests is considered small and is not likely to adversely affect the patient or their disease. However, the effects of radiation add up over a lifetime. It is possible that having several of these tests may add to the patient's risk of injury or disease. When deciding to enter this study, the patient should think about your past and future contact with radiation. Examples of contact with radiation include x-rays taken for any reason or radiation therapy for cancer treatment.

There are no other known risks involved in this study, aside from the minor inconvenience of completing questionnaires. One possible risk related with the patient's

participation in this study is the loss of privacy. To reduce these risks, all of the information collected will be de-identified (the patient will be assigned a study number and all data will be linked to that number and not the patient's name) and stored in a password protected file on a password protected computer. Some of the questions asked may be upsetting, or the patient may feel uncomfortable answering them. If the patient does not wish to answer a question, they may skip it and go to the next question.

Additionally, both stems used in this study are standard surgical stems used by orthopaedic surgeons. Therefore, there are no additional risks involved in the use of these stems for this study.

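### Stress-shielding is read from plain films that show stem length, with no masking step, so the comparison is open to detection bias; coded, cropped proximal images would reduce this at little cost

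*Combined protocol and SAP*

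**What the plan says.** The Introduction (Section 1.0) describes the design in these terms: "By conducting a single blinded, prospective, randomized investigation of two stems of varying length with equal metallurgy, coating, and proximal geometry". No section says who is blinded.

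Section 5.0 lists the films, "X-ray analysis includes antero-posterior pelvis, and lateral hip radiographs", and sends them to an outside centre "for analyses using the EBRA-FCA software". Section 6.0 connects EBRA-FCA with implant migration. For stress-shielding, Section 6.0 says only this: "Antero-posterior pelvis and lateral hip radiographs will show patterns of stress-shielding". It gives no grading scale, zones, reader or number of readers. Neither section describes masking or cropping of films. Section 5.0 replaces the patient's name with a study number, which does not hide an implant on an image.

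The Introduction also states an expectation for this outcome. Of the comparator it says: "Standard length stems cause stress-shielding in Gruen zones 1 and 7". Of the experimental device it says: "short stems can prevent excessive bone loss secondary to stress shielding".

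**The concern.** Three conditions that together favour detection bias are present for this one outcome. The reading has no defined scale, so the reader must use judgement. The image shows which stem the patient has. The document says in advance which stem should look better.

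If a reader who can see the arm scores doubtful films in the expected direction, the trial can report less stress-shielding with the short stem when there is no true difference. Less bone loss from stress-shielding is one of several advantages that Section 1.0 claims for short stems, so a biased reading would bear on the viability question in Section 2.0. Recruiting more patients does not remove this kind of error.

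**Working it through.** The documents state no figure for this outcome (no rate, test, alpha or power), so there is nothing to reproduce. The check is mainly a reading of the sections together, followed by an illustration on assumed values.

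**Does the film reveal the arm?** The Introduction says the trial compares "two stems of varying length with equal metallurgy, coating, and proximal geometry". Length is the stated difference. An uncropped film that includes the stem tip therefore shows the arm to anyone who can tell the two lengths apart.

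**Does any step prevent this?**
- The opaque envelopes in Section 5.0 conceal allocation until the femur is being prepared. They do nothing afterwards.
- The study number removes the name but not the stem.
- The off-site analysis is described for migration, not for stress-shielding.

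No other step is described.

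**Could the arm be hidden?** The Introduction says proximal geometry is equal and places the expected stress-shielding in Gruen zones 1 and 7, in connection with proximal loading. On those statements, an image cropped above the short-stem tip would keep proximal bone and remove the feature that separates the arms. The documents do not give stem lengths, zone boundaries or the position of the short-stem tip. Whether one crop level works in every patient cannot be settled from the text.

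**How much could a reading shift matter?** Inputs:
- From Section 5.0: 50 patients, half per stem, so 25 per arm.
- Assumed: a yes/no reading, the same true rate p in both arms (30% or 50%), and a reading shift d that makes the apparent rate p + d/2 with the standard stem and p - d/2 with the short stem.
- Assumed: a two-sided 5% test.

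The false-positive chance is the sum, over all counts i and j from 0 to 25, of Bin(i; 25, p + d/2) x Bin(j; 25, p - d/2), taken over the pairs where the test rejects. The uncorrected chi-square rejects when |i - j|/25 divided by sqrt(q(1 - q) x 2/25) exceeds 1.96, with q = (i + j)/50. Fisher's exact test rejects when its p-value is at most 0.05.

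Example: p = 30% and d = 10 points gives apparent rates of 35% and 25%.

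| True rate | Shift | Chi-square | Fisher |
|---|---|---|---|
| 30% | 0 | 5.4% | 2.3% |
| 30% | 10 points | 12.6% | 6.6% |
| 30% | 20 points | 35.2% | 23.1% |
| 50% | 0 | 6.5% | 3.3% |
| 50% | 10 points | 13.3% | 7.9% |
| 50% | 20 points | 33.6% | 23.7% |

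The Synopsis gives 75 subjects instead of 50. With 38 standard and 37 short stems, a 20-point shift gives 47% (p = 30%) and 46% (p = 50%) by chi-square, or 42% and 37% by Fisher. The larger sample makes a false finding more likely, because the shift is a bias and not noise.

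**The case against.** **No contradiction with the blinding label.** A reader might infer that the trial promises blinding and then breaks the promise. The documents do not support that. The Introduction does not say who is blinded, and opening envelopes in the operating room is compatible with blinding the patient only. What stands is that the blinded party is unspecified and assessor masking is absent.

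**The reader is not said to know the arm.** That is correct. The plan names no stress-shielding reader and does not say that the reader is told the allocation. The exposure is inferred from visible stem length and the lack of any masking step. That the reading is subjective is likewise inferred, from the reference to patterns and the absence of a scale.

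**The expectation is limited.** Overall, the Introduction expects the stems to be equally effective. It also lists other short-stem benefits, such as less soft-tissue damage, faster recovery and fewer intraoperative fractures, and it ranks none of them. A reader might take stress-shielding to be the main claimed advantage, but no section says so. On this one outcome, though, the stated prediction does favour the short stem.

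**Cropping may not work in every patient.** This stands. The tip position is not given, a reader who has already seen the full films in clinic may remember some, and the distal femur drops out of the masked reading. Cropping is a practical improvement that needs a feasibility check.

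**The illustration assumes what it shows.** This also stands. The direction and size of the shift are put in by hand, and the plan specifies neither a yes/no outcome nor a test. The figures show how sensitive a trial of this size is to a reading shift. They are not evidence that a shift will occur, nor that the comparison would be worthless.

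**Conclusion.** The point holds as a gap in outcome assessment. As written, the plan allows stress-shielding to be judged without a scale from films that display the arm, on an outcome for which it predicts a direction. That leaves the comparison open to detection bias, and the plan should be amended.

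The conclusion rests on two statements in the document, that the stems differ in length and that EBRA-FCA serves migration, and on its silence about masking. The bias cannot be sized from the documents. The false-positive chances of about 13% (chi-square) or 7-8% (Fisher) for a 10-point shift with 25 per arm depend wholly on assumed rates, an assumed shift and an assumed test.

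**What to change.** Amend Sections 5.0 and 6.0 as follows.

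1. Name the stress-shielding reader from existing study staff, preferably someone who was not the operating surgeon.
2. Have that reader score copies of the films that carry a random code, are in random patient order, and are cropped to the proximal femur above the short-stem tip. Someone else should prepare the copies.
3. Compare each 2-year film with the same patient's immediate post-operative film on a fixed ordinal scale. Use proximal medial and lateral regions defined by the same anatomical landmarks in both arms, and compare the arms on that score.
4. Before use, check on a few existing films that one crop level keeps the proximal region and excludes the short-stem tip. If it fails in some patients, report how many readings were unmasked.
5. Describe distal changes from the full films and label them as unmasked.
6. State who is blinded under the single-blind label.

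The cost is a short amendment and a little image preparation, with no new film or visit. The downside is that there is no masked reading of the distal femur.

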7.0 DATA COLLECTION & RECORD KEEPING

All information regarding the nature of the proposed investigation provided to the investigator (with the exception of information required by law or regulations to be disclosed to the IRB, the subject, or the appropriate regulatory authority) will be kept in confidence by the principal investigator. All personal information will be treated as strictly confidential and not made publicly available. All records are stored in a locked filing cabinet and password protected computers which are accessed only by the Principal Investigator and Study Coordinators. All identifiable data will be destroyed a year after the study is complete.

